6.6. Efficacy Endpoints (FAS、PPS)

6.6.1. Primary Efficacy Endpoints

Table 18 Device procedural success (18)

Project	Indicator	FAS	Control Group	PPS	Control Group
		Experimental group		Experimental Group	
Device	Success n(%)				

Project	Indicator	FAS		PPS	
		Experimental group	Control Group	Experimental Group	Control Group
procedural Rate	Failure n(%)				
	Total (Missing)				
	Single-group				
	success rate 95% CI				
	Statistic (CMH)				
	P-value				

Note 1: Device procedural success (by lesion level) requires simultaneous fulfilment of the following conditions: a. Successful completion of the entire balloon dilatation procedure, including delivery, lesion crossing, inflation, deflation, retraction, and withdrawal; b. Immediate post-PCI target lesion residual stenosis $\leq 30\%$ (for in-stent restenosis and drug-coated balloon restenosis lesions, post-procedural residual stenosis $< 50\%$). a. Partial analysis presented in Table 20: Device Evaluation; b. Partial analysis presented in Table 21: Immediate Post-PCI Target Lesion Residual Stenosis.

Note 2: For patients in the FAS cohort where the primary efficacy endpoint was not observable, worst observation carried forward was applied; subjects where assessment was inconclusive were counted as failing device use success.

Table 19 Device Success Rate (Lesion Level) Hypothesis Test

Population	Parameter	Experimental group n(%)	Control Group n(%)	Difference in Rates		P	Non-inferiority margin
				Between Groups	Difference in rates between groups Two-sided 95% CI		
FAS	Experimental group - Control group						-10%
PPS	Experimental group - Control group						-10%

Note 1: Rate difference = Experimental group - Control group. The non-inferiority margin is -10%. The 95% confidence interval for the rate difference was calculated using the XX method.

Note 2: The lower limit of the 95% confidence interval for the intergroup success rate difference exceeds -10%, establishing the non-inferiority hypothesis.

Table 20 Device Evaluation (Lesion Level)

Item	Indicator	FAS		PPS	
		Experimental Group	Control Group	Experimental Group	Control group
Device usage success	Yes n(%)				
	No n(%)				

Item	Indicator	FAS		PPS	
		Experimental Group	Control Group	Experimental Group	Control group
Balloon successfully advanced to lesion	Total (Missing)				
	Statistic				
	P-value				
	Yes n (%)				
	No n(%)				
	Total (Missing)				
Balloon successful passage through lesion	Statistic				
	P-value				
	Yes n (%)				
	No n(%)				
	Total (Missing)				
	Statistic				
Whether the balloon successfully covered the lesion	P-value				
	Yes n (%)				
	No n(%)				
	Total (Missing)				
	Statistic				
	P-value				
Balloon Retraction Success	Yes n (%)				
	No n(%)				
	Total (Missing)				
	Statistic				
	P-value				

Note: Device evaluation analysis is based on trial balloon performance assessments collected via EDC.

Table 21 Immediate postprocedure residual stenosis at target lesion (lesion level)

Item	Indicator	FAS		PPS	
		Experimental group	Control Group	Experimental Group	Control Group
De-nove lesion	N(Missing)				
	Mean (SD)				
	Median				
	Q1, Q3				
	Min, Max				

Item	Indicator	FAS		PPS	
		Experimental group	Control Group	Experimental Group	Control Group
De-novo lesion - Postprocedure residual stenosis in target lesion $\leq 30\%$	Statistic				
	P-value				
	Yes n(%)				
	No n(%)				
	Total (Missing)				
	Statistical measure				
	P-value				
	In-stent restenosis Restenotic lesion				
	N(Missing)				
	Mean (SD)				
In-stent restenosis Postprocedure residual stenosis degree of restenotic lesion $< 50\%$	Median				
	Q1, Q3				
	Min, Max				
	Statistic				
	P-value				
	Yes n(%)				
	No n(%)				
	Total (Missing)				
	Statistical measure				
	P-value				
Drug-eluting stent restenosis lesions	N(Missing)				
	Mean (SD)				
	Median				
	Q1, Q3				
	Min, Max				
	Statistic				
	P-value				
	Postprocedure residual stenosis rate of drug-eluting balloon restenosis lesions $< 50\%$				
	Yes n(%)				
	No n(%)				
Postprocedure residual stenosis rate of drug-eluting balloon restenosis lesions $< 50\%$	Total (Missing)				
	Statistical measure				
	P-value				

Note 1: Primary lesion refers to a lesion with stenosis demonstrated by coronary angiography, excluding in-stent restenosis or drug-eluting balloon restenosis.

Note 2: Analysis of restenosis severity was based on core laboratory data: residual stenosis percentage in the post-procedural segment.

Table 22 Device Success Rates by Centre (Lesion Level)

Research Centre	Item	Indicator	FAS Experimental Group	Control Group	PPS Experimental Group	Control Group
01	Device usage success rate	Success n(%) Failure n(%) Total (Missing)				
02	Device Usage Success Rate	Success n(%) Failure n(%) Total (Missing)				
.....	Success of instrument use	rate Success n(%) Failure n(%) Total (Missing)				

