## 6.2 Analysis Data Sets

Statistical analysis will be carried out on the basis of the following analysis populations. The analysis populations will be clearly defined before the start of statistical analysis. And the analysis populations in this study include:

- (1) Full Analysis Set (FAS): the set of subjects determined following the intent-to-treat (ITT) principle refers to the data set constituted by all subjects who participate in the randomized study and receive the investigational product. The worst observation carried forward (WOCF) is used for imputation of the patients in whom the Primary efficacy endpoint is unable to be observed.
- (2) Per-Protocol Set (PPS): refers to the subgroups of treatment population where the study has been completed with the major protocol violations excluded (which means that the subjects violate the inclusion criteria or exclusion criteria, etc.).
- (3) Safety set (SS): refers to the subject dataset using investigational medical devices and having recorded safety endpoints.

The efficacy analysis will be performed based on the FAS and PPS. All baseline demographic data analysis will be performed on the FAS while the safety evaluation will be on the SS.

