### **6.4.3 Significance Level and Power of Clinical Study**

In this trial, for the primary endpoint, the significance level of statistical test is 0.025% one-sided, and the power of test is taken as 80%. For other indicators, the significance level of statistical test is taken as 0.05 two-sided.

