## 6.5 Missing Data and Outliers

Method for the treatment of missing data: The missing data will be processed according to the division of the data set; primary efficacy data will be imputed with the use of the WOCF (Worst Observation Carry Forward).

Wrong data handling method: In the process of data management, the quality management will be performed for the data in the database, wrong data found will be questioned in the form of Query to investigators, and the wrong data will be adjusted according to the written reply of investigators until all wrong data is corrected before locking the database.

Unreasonable data handling method: In the process of data management, the data in the database will be checked logically, unreasonable data found will be questioned in the form of Query to investigators, and the unreasonable data will be adjusted according to the written reply of investigators until all unreasonable data is solved before locking the database.

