1.5. Sample size

Based on literature review, clinical experience, and results from studies evaluating scoring balloon catheters for coronary artery disease, it is hypothesised that the study group's Sino scoring balloon dilation catheter will demonstrate comparable efficacy to the control group's Goodman coronary NSE balloon catheter, with an anticipated device success rate of 96%. Considering factors such as operator skill variation, lesion complexity, and subject comorbidities and disease severity, the sponsor, clinical experts, investigators, and statisticians jointly determined a non-inferiority margin Δ of -10%, a one-sided test α of 0.025, and a test power (1- β) of 0.8. PASS software calculations yielded a total sample size of 122 subjects, with 61 subjects in each group. Accounting for a 10% dropout rate, the trial requires 136 subjects, distributed as 68 in each group. The sample size calculation formula is as follows:

$$n_T = n_C = \frac{\left(Z_{1-\frac{\alpha}{2}} + Z_{1-\beta}\right)^2 [P_C(1 - P_C) + P_T(1 - P_T)]}{(|D| - \Delta)^2}$$

Where n_T and n_C denote the sample sizes for the treatment and control groups respectively, $Z_{1-\frac{\alpha}{2}}$ and $Z_{1-\beta}$ represent the quantiles of the standard normal distribution, P_T and P_C denote the expected event rates for the treatment and control groups respectively, $|D| = |P_T - P_C|$ denotes the absolute difference in expected rates between the two groups, and Δ denotes the non-inferiority margin, taken as a negative value.

This trial will be conducted concurrently across multiple clinical trial sites. In principle, enrolment numbers will be distributed as evenly as possible among centres to ensure adequate representativeness. However, considering feasibility and enrolment progress, adjustments to enrolment quotas for participating sites will be made based on actual circumstances, striving to maintain balanced enrolment scales across centres. The final enrolment size for any single centre shall not exceed 50% of the total number of cases.

2. Evaluation Criteria

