
4. Handling of missing data

For patients in the FAS who did not have an observation for the primary efficacy endpoint, worst observation carried forward was applied. For target lesions where device success could not be determined, imputation was performed as 'device failure'. No imputation was performed for secondary endpoints or efficacy endpoint in the PPS. Missing safety data were not imputed.

5. Statistical Analysis Methods

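### SAP section 4 fails the undetermined lesion, Table 18 Note 2 fails the subject: a two-lesion subject can add one or two failures to a lesion-level primary endpoint

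*SAP*

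**What the plan says.** Device success is defined and analysed at lesion level (Protocol 5.3.1; SAP 2.1.1 and 5.4.1). Inclusion criterion 6 (Protocol 5.2.1) allows a planned intervention at up to two lesions, and SAP Table 11 has a row for subjects with two target lesions.

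The rule for an outcome that cannot be determined appears in three forms:

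- **SAP section 4 (Handling of missing data), unit = lesion.** "For target lesions where device success could not be determined, imputation was performed as" device failure. The sentence before it applies worst observation carried forward (WOCF) to patients in the full analysis set (FAS) without a primary observation. The section also says that the per-protocol set (PPS) has no imputation.
- **SAP 6.6.1, Table 18 Note 2, unit = subject.** After repeating WOCF, it states that "subjects where assessment was inconclusive were counted as failing device use success". It does not say what happens to such a subject's other lesion.
- **Protocol 6.2 and 6.5, unit = patient or none.** Protocol 6.2: "The worst observation carried forward (WOCF) is used for imputation of the patients in whom the Primary efficacy endpoint is unable to be observed". Protocol 6.5: "primary efficacy data will be imputed with the use of the WOCF (Worst Observation Carry Forward"). Neither defines the imputed value as failure. SAP section 3 repeats the patient-level WOCF sentence.

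**The concern.** The unit of the imputation rule should match the unit of the endpoint. Take a subject with two target lesions, one observed as a success and one undetermined. Under SAP 4 the subject contributes one failure and one success. Under Note 2 taken at its word the subject fails, so the observed success is overwritten and two failures are counted. Note 2 stands under the table that reports the primary result, where a programmer is likely to look.

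The Protocol does not settle the matter. Residual stenosis is read immediately after PCI, so the lesion has no earlier observation to carry forward.

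At a 96% expected success rate only a handful of failures are expected in each arm, so one lesion more or less can matter. The trial is open-label (Protocol 5.1). If the unit is left open, it could be chosen by someone who knows which arm contains the affected subjects.

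**Working it through.** **1. The plan's own sample size.** Inputs from Protocol 6.1.1 and SAP 1.5: success 96% in both arms, margin -10%, one-sided alpha 0.025, power 80%. The Protocol gives the squared sum of normal quantiles as 7.85.

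n per group = 7.85 × (0.96×0.04 + 0.96×0.04) / 0.10² = 7.85 × 0.0768 / 0.01 = 60.3, rounded up to 61. With 10% dropout, 61/0.9 = 67.8, rounded up to 68. Both stated figures reproduce.

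**2. Failures added by one affected subject** (one success, one undetermined lesion): SAP 4 gives 1; Note 2 read literally gives 2. For single-lesion subjects both give 1.

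**3. Can 1 versus 2 change the verdict?** Assume 68 subjects per arm, 14 of them with two lesions, so 68 + 14 = 82 lesions per arm, and 3 control failures (79/82 = 96.3%). An example with 68 lesions per arm would not serve: it leaves no two-lesion subjects and the rules could not differ. SAP Table 19 leaves the interval method as a placeholder, so three methods are shown. Lower limit of the two-sided 95% interval, test minus control:

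| Test failures | Wald | Newcombe | Miettinen-Nurminen |
|---|---|---|---|
| 3 | -5.75% | -6.98% | -7.06% |
| 4 | -7.40% | -8.62% | -8.75% |
| 5 | -9.02% | -10.22% | -10.37% |
| 6 | -10.61% | -11.76% | -11.94% |

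Newcombe lower limit = (pT - pC) - √[(pT - LT)² + (UC - pC)²], where LT and UC are Wilson limits. The control upper limit is 0.98748, so UC - pC = 0.02407.

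- 4 failures: pT = 78/82 = 0.95122, LT = 0.88119; limit = -1.2195% - 7.4054% = -8.62%, pass.
- 5 failures: pT = 77/82 = 0.93902, LT = 0.86508; limit = -2.4390% - 7.7763% = -10.22%, fail.

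With three other test failures, one affected test-arm subject therefore passes under SAP 4 and fails under literal Note 2 (Newcombe or Miettinen-Nurminen). With Wald the same flip occurs between 5 and 6.

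**4. How often, given exactly one affected test-arm subject?** With 96% true success in both arms and independent lesions, the chance that 1 versus 2 changes the verdict at 82 lesions per arm is 15% (Wald) to 18% (the other two). Across 75 to 102 lesions per arm and all three methods it is 10% to 21%.

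**5. How often is anyone affected?** Let s be the share of two-lesion subjects and u the share of undetermined lesions. P(at least one of 136) = 1 - [1 - s·2u(1-u)]^136.

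- s = 10%, u = 0.5%: 1 - (1 - 0.000995)^136 = 13%
- s = 10%, u = 1%: 1 - (1 - 0.00198)^136 = 24%
- s = 10%, u = 2%: 1 - (1 - 0.00392)^136 = 41%
- s = 20%, u = 5%: 1 - (1 - 0.019)^136 = 93%

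**6. Whole-trial disagreement.** Simulation with 68 subjects per arm, 96% success, lesions independent and undetermined at random, Newcombe limit, both rules applied to the same data:

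| s | u | Opposite verdicts |
|---|---|---|
| 10% | 0.5-1% | about 2-3% |
| 10% | 2% | 5% |
| 20% | 5% | 11% |

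The pass probability under the lesion and subject rules is 0.648 and 0.627 at s = 10%, u = 2%, and 0.576 and 0.528 at s = 20%, u = 5%.

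**The case against.** The best defence is that there is no second rule. Note 2 sits under a lesion-level table and speaks of device success, which is defined per lesion. It never says that an observed lesion is overwritten. SAP 4 is the dedicated missing-data section, and Note 2 can be read as a loose restatement of it, which gives one failure. This is a fair reading and may be the intended one. It does not remove the need to correct the note, because its literal wording gives a different count in the primary table.

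Second, undetermined lesions may be rare. Device handling is recorded during the procedure and the angiogram is taken immediately afterwards. A delivery or withdrawal failure already settles the lesion as failed, so an undetermined result mostly needs unusable images. This stands, and it is why the range above starts at 0.5%.

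Third, the effect is narrow. The PPS has no imputation and is reported alongside the FAS. Protocol 6.4.7 requires the SAP to be final before database lock with changes recorded, which limits the scope for a convenient choice. Both points stand.

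A reader might also infer a third count of zero failures: under bare WOCF, the worst observed result of the affected subject is the other lesion's success, which is then carried across. The Protocol wording alone does not exclude this. The SAP does: section 4 imputes the undetermined target lesion as failure, Note 2 also pairs WOCF with failure, and neither document describes carrying one lesion's result to another.

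**Conclusion.** The inconsistency is real and lies in the rule for the primary endpoint: SAP 4 works per lesion, Table 18 Note 2 per subject, and the Protocol gives a patient-level WOCF that does not fit a single assessment. The live conflict is one failure versus two.

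It matters only in the FAS, only for a two-lesion subject with exactly one undetermined lesion, and only when the result is near the margin. Opposite verdicts occur in about 2-3% of trials at the low end of the assumed range and 5-11% at the higher end; the chance of at least one affected subject runs from 13% to 93%. These figures rest on assumed shares of two-lesion subjects and undetermined lesions, on independence between lesions and on the Newcombe method, none of which the documents specify.

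The documents do not support saying that the SAP definitely fails both lesions, or that the unit has been or will be chosen to favour an arm. The wording should still be corrected: its effect is bounded, but it concerns the primary count.

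**What to change.** In SAP Table 18 Note 2, replace 'subjects' by 'target lesions'. State there and in SAP 4 that each undetermined target lesion counts as one device failure and that the subject's other lesion keeps its observed result. Align the WOCF wording in SAP 3, SAP 4 and Note 2, and in Protocol 6.2 and 6.5, with that lesion-level failure rule.

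The cost is a few words in the SAP and a one-line protocol clarification, with no new data and no change to the sample size. It should be done before database lock.

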6.6.2. Secondary efficacy endpoint

Table 23 Procedure success rate (subject level)

Item	Indicator	FAS Experimental Group	Control Group	PPS Experimental Group	Control Group
Procedure success rate	Success n(%) Failure n(%) Total (Missing) Statistical measure P-value				

Note: Procedure success (subject level) requires simultaneous fulfilment of the following conditions: a. At least one target lesion residual stenosis $\leq 30\%$ immediately after PCI (postprocedure residual stenosis $< 50\%$ for ISR and drug-coated balloon restenosis lesions); No major adverse cardiac events (MACE) during postprocedure hospitalisation: all-cause mortality, myocardial infarction (MI), and target lesion revascularisation (TLR).

Table 24 Immediate postprocedure target lesion residual stenosis degree (subject level)

Item	Indicator	FAS Experimental group	Control Group	PPS Experimental Group	Control Group
Postprocedure Immediate Lesion Stenosis Meeting Criteria	Yes n(%) Target Residual Degree No n(%) Total (Missing) Statistical measure P-value				

Note: Target achievement denotes at least one target lesion with residual stenosis $\leq 30\%$ immediately postoperatively (ISR and drug-eluting balloon restenosis lesions with residual stenosis $< 50\%$ postoperatively). Analysis of target lesion residual stenosis is based on core laboratory data: residual stenosis within the postprocedure segment in XXX.

Table 25 Major Adverse Cardiac Events (MACE) During Postoperative Hospitalisation (Subject Level)

Item	Indicator	FAS		PPS	
		Experimental Group	Control Group	Experimental Group	Control Group
Incidence of MACE	Yes n(%)				
	No n(%)				
	Total (Missing)				
	Statistic				
	P-value				
All-cause mortality	Yes n (%)				
	No n(%)				
	Total (Missing)				
	Statistic				
	P-value				
Myocardial infarction (MI)	Yes n (%)				
	No n(%)				
	Total (Missing)				
	Statistic				
	P-value				
Target lesion revascularisation (TLR)	Yes n (%)				
	No n(%)				
	Total (Missing)				
	Statistic				
	P-value				

Note: Analyses for all-cause mortality, myocardial infarction (MI), and target lesion revascularisation (TLR) were based on death reports, myocardial infarction forms, and revascularisation forms.

Table 26 Major Adverse Cardiac Events (MACE) during Postprocedure Hospitalisation (Subject Level) - Primary Lesion

Table 27 Major Adverse Cardiac Events (MACE) During Postprocedure Hospitalisation (Subject Level) - Restenotic Lesion

6.7. Safety Endpoints (SS)

6.7.1. Target lesion failure (TLF) incidence

Table 28 Target lesion failure (subject level)

Item	Indicator	Experimental group	Control Group	Total
TLF Occurrence	No n(%)			
	Yes n(%)			
	Total (Missing)			
	Statistic			
	P-value			
Cardiac death	No n(%)			
	Yes n(%)			
	Total (Missing)			
	Statistic			
	P-value			
Occurrence of target myocardial infarction	No n(%)			
	Yes n(%)			
	Total (Missing)			
	Statistic			
	P-value			
Whether clinically driven target lesion revascularisation occurred	No n(%)			
	Yes n(%)			
	Total (Missing)			
	Statistic			
	P-value			

Note: Any occurrence of the following events is considered a TLF (subject level): a. Cardiovascular death (if cause of death is uncertain, it is also considered cardiovascular death); b. Target Vessel-Related Myocardial Infarction (TV-MI); c. Clinically-Driven Target Lesion Revascularisation (CI-TLR). Analysis of cardiac death, target vessel-related myocardial infarction, and clinically-driven target lesion revascularisation was based on death reports, myocardial infarction reports, and revascularisation reports.

6.7.2. Incidence of the patient-oriented composite endpoints (PoCE)

Table 29 Patient-oriented composite endpoints (Subject level)

Item	Indicator	Experimental group	Control Group	Total
Occurrence of PoCE	No n(%)			
	Yes n(%)			
	Total (Missing)			
	Statistic			
	P-value			
All-cause mortality	No n(%)			

Item	Indicator	Experimental group	Control Group	Total
Myocardial infarction	Yes n(%)			
	Total (Missing)			
	Statistic			
	P-value			
	No n(%)			
	Yes n(%)			
	Total (Missing)			
	Statistic			
	P-value			
	Whether revascularisation occurred			
Whether revascularisation occurred	No n(%)			
	Yes n(%)			
	Total (Missing)			
	Statistic			
	P-value			

Note: Any occurrence of the following events was considered a PoCE: a. All-cause mortality; b. All myocardial infarctions; all revascularisation events, including target lesion revascularisation (TLR), target vessel revascularisation (TVR) and non-target vessel revascularisation. Analysis of all-cause mortality, myocardial infarction, and revascularisation was based on death reports, myocardial infarction reports, and revascularisation reports.

6.7.3. Procedure-related complications

Table 30 Procedure-related complications

Item	Indicator	Experimental group	Control Group	Total
Presence of procedure Complications	None n(%)			
	Yes n(%)			
	Total (Missing)			
	Statistical measure			
	P-value			
Balloon rupture	None n(%)			
	Yes n(%)			
	Total (Missing)			
	Statistic			
	P-value			
Puncture oedema	None n(%)			
	Yes n(%)			
	Total (Missing)			
	Statistic			
	P-value			
Vascular perforation	None n(%)			
	Yes n(%)			
	Total (Missing)			

Item	Indicator	Experimental group	Control Group	Total
Vascular dissection	Statistic			
	P-value			
	None n(%)			
	Yes n(%)			
	Total (Missing)			
Acute occlusion	Statistic			
	P-value			
	None n(%)			
	Yes n(%)			
	Total (Missing)			
Vasospasm	Statistic			
	P-value			
	None n(%)			
	Yes n(%)			
	Total (Missing)			
Thrombosis	Statistic			
	P-value			
	None n(%)			
	Yes n(%)			
	Total (Missing)			
Other	Statistic			
	P-value			
	None n(%)			
	Yes n(%)			
	Total (Missing)			
	Statistic			
	P-value			

